9.2 Patient Timeline from Eligibility to first 6 month appointment

• Day 0: Screening visit: Seen in clinic and X-rayed to determine eligibility and given information

BASIS Study

- Week 0-7: Telephone call from Research Team+ e-consent + randomisation (may be in person if patient prefers at clinic visit). This may be delayed if the patient is sent for a spinal MRI
- Week 2-6: Brace measurement (after randomisation)
- Week 4-8: Brace fitting
- In brace XR within 6 weeks of brace fitting
- Week 26: First follow-up 6 months after randomisation.

9.3 Unscheduled visits

Participants may be seen at additional visits outside those scheduled for the study, but these visits would be part of usual care. Any complication identified at additional usual care visits, will be documented in the CRF. Patients will be asked at each follow up visit if they have experienced any AEs since their previous study visit.

9.4 Procedures for assessing efficacy

Efficacy is assessed by measuring the percentage correction of Cobb angle in brace compared with the most recent standing radiograph taken at the appointment before randomisation. This is determined by curve flexibility and the type of brace used (NTB will have a higher correction in brace as the radiograph is taken supine). The DMEC will review this efficacy data at each meeting for the new intervention of the NTB and will feedback any training suggestions to the Trial Management Group (TMG).

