An alternative to the FTB, is a brace only worn at night time (a "night-time brace", or NTB). Such a brace would be 'hidden' from daily life and could significantly improve quality of life and other psychological effects of bracing in this population whilst not increasing the need for surgery. This may therefore have better compliance, with a recent study prescribing a NTB for 8 hours per day and observing a mean wear time of 7.2 hours per day (13). Instead of 'holding' the spine to prevent deformity, these attempt to apply a force to the spine to 'over correct' the deformity. A NTB has several potential advantages over a FTB: (1) curves reduce in size as gravity is eliminated (curves are 10 degrees smaller lying down compared to standing (14)); (2) the brace comes down further over the pelvis than can be achieved for a FTB allowing a longer lever arm and more corrective force applied to the spine, which would make these braces difficult to stand and sit in; (3) the pressure applied to the spine is more constant whilst in bed but tends to reduce over time for braces worn during the day in the upright position (15); and (4) growth occurs mainly at night with higher levels of growth hormone (16).

BASIS Study

The NTB was introduced with the Charleston brace in 1978 (17). This brace is made from a plaster cast model or measurements with the patient laterally flexed towards the side of the curve which produces correction in single curves. However, it is biomechanically less suitable for double curves which limits its use (18) and when double curves are treated in a Charleston brace, success is less than for single curves (19). Low quality comparative studies of Charleston NTB with rigid FTB suggest the Charleston brace may be less effective especially in larger curves (15,16). For these reasons, we will not be using the Charleston brace in this study.

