6.3 Both braces

Sites should aim to have patients in brace within 8 weeks of consultant referral to reduce the risk of curve progression before bracing.

Following randomisation, the patient will attend a first clinic appointment with the Orthotist where they will be measured for their allocated brace. From these measurements, the brace will be designed and manufactured. The patient will return for a brace fitting appointment where the brace will be 'fine-tuned' (with pads if required). Once the brace is fitted, an in brace spinal radiograph either at the initial fitting or within the first 6 weeks in brace is obtained to ensure good curve correction. This will be done standing for the FTB and supine for the NTB. Further adjustments are permissible as required. The patient will be followed up as per local protocol, including regular brace check, adjustment, download of compliance data as required, and complications noted. A standing spine x-ray out of brace will be performed with an in-brace x-ray if required to guide brace adjustment. The patient will be reviewed by the spinal team to evaluate Cobb angle and skeletal maturity (Risser sign). All patients will have contact details for the spinal team, research team and orthotist for advice or concerns.

Braces will be renewed when required due to growth of the child. When a brace is renewed, the same protocol described above will be followed. Bracing will continue

until the patient reaches skeletal maturity (Risser 4 (girls) or Risser 5 (boys)), or until surgery is required. At this point, the brace can be discontinued.

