8.2 Secondary outcomes/endpoints

Patient-reported outcomes (collected throughout the study unless stated otherwise):

- 1. Scoliosis Research Society 22 questionnaire (41);
- 2. Paediatric health related quality of life, measured using the CHU9D (42);
- 3. Bad Sobernheim Stress Questionnaire (BSSQ) (43), a brace specific questionnaire assessing the psychological effects of bracing;
- 4. Revised Children's Anxiety and Depression Scale (RCADS 25) (44);
- 5. PROMIS Paediatric Sleep Disturbance Short Form 4a (45);
- 6. PROMIS Paediatric Sleep Related Impairment Short Form 4a
- 7. Modified Client Satisfaction with Device module of the Orthotics and Prosthetics Users' Survey (CSD-OPUS) (46)
- Educational information assessed using a bespoke questionnaire after GCSE results;

Parent Questionnaires (collected throughout the study unless stated otherwise):

- 9. Patient Cost Questionnaire, using a bespoke questionnaire
- 10. Resource Use Questionnaire, using a bespoke questionnaire;
- 11. School attendance (only during bracing).

Clinical (collected throughout the study unless stated otherwise):

12. Radiological measures from out-of-brace spinal radiographs (with correction of any leg length inequality): Cobb angle, curve type, curve apex, Risser sign, in-brace

Cobb angle, frontal plane balance, apical vertebral rotation, apical vertebral translation;

- 13. In-brace correction, measured for all new braces as the percentage Cobb angle correction in-brace compared with out-of-brace. The in-brace x-ray will be performed standing for FTB and supine for NTB. This reflects brace quality and curve flexibility. Bracing is more likely to fail when there is a lower initial in-brace correction of the curve (47,48). In-brace correction will be monitored during the trial by the DMEC for the new intervention of the NTB and will feedback any training suggestions to the Trial Management Group (TMG);
- 14. Menarchial age;
- 15. Details of any surgery for scoliosis correction;
- 16. Other treatments prescribed to treat scoliosis, e.g. scoliosis specific exercises;
- 17. Complications (e.g. skin irritation) and Serious Adverse Events;
- Brace compliance, assessed using the implantation of a temperature sensor in the FTB or NTB (collected only during bracing);
- 19. Treatment switching, including reason for doing so (bespoke questionnaire).

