of spinal patients currently used to evaluate surgical patients and is familiar to the clinical staff in each centre, and an efficient means of follow-up in routine use. The central team will ensure data quality and data completeness is optimised.

Data Management (CRF design, data cleaning and validation) will be provided by the CTRU. Project-specific procedures for data management will be detailed in a data management plan.

Data will be collected in three phases:

Phase 1: Pre-skeletal maturity

Whilst in brace, patients will be seen routinely every 6-months for clinical monitoring, anchored from the date of randomisation. Routinely collected out-of-brace spinal radiographs will be taken at each visit in order to measure the Cobb angle (primary outcome). This is accepted as best practice guidelines for bracing in AIS (49). Such radiographs will be sent through the Image Exchange Portal and clinical data entered onto the BSR by research staff. Before the 6 month visit, parents and/or patients will be emailed a link to the questionnaires in the BSR which would be labelled for either 'patient' or 'parent' completion. If not completed, they will use a computer or tablet in the clinic to complete the questionnaires, with paper forms available as a back-up. Questionnaire completion will be checked and chased by mail or telephone as required.

There are a few scenarios:

- If the primary outcome is reached (progression to 50 degrees) before skeletal maturity, follow up will continue via email link to the BSR which will collect PROMs every 6 months
- If the patient has surgery, radiographs and questionnaires will be collected at routine post-operative clinic follow-up at 6-8 weeks, 1 year and 2 years after surgery.
- If the patient changes from NTB to FTB (cross-over), the reason will be recorded. Cross-over in the other direction is not allowed. Follow-up will continue unchanged.
- If the patient stops bracing altogether, follow-up will be continued.
- Rarely, during follow-up, patients will develop symptoms that prompt a spinal MRI scan. If this shows spinal dysraphism (dilated central canal is not defined as spinal dysraphism) as the cause for their scoliosis, the patient will continue in the trial for analysis on 'intention to treat' (ITT) but will be excluded from the per protocol (PP) analysis.

Phase 2: Post-skeletal maturity

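### Section 9.4 ties percentage in-brace correction to the pre-randomisation film, so for a renewed brace the value mixes brace correction with curve change since baseline

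*Protocol*

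**What the plan says.** Three parts of the protocol bear on this measure.

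- **Section 8.2**, in the list of clinical secondary outcomes, defines it as "In-brace correction, measured for all new braces as the percentage Cobb angle correction in-brace compared with out-of-brace". It names no date for the out-of-brace film. It describes the result as reflecting both the quality of the brace and the flexibility of the curve.
- **Section 9.4** gives the percentage correction a single reference: "compared with the most recent standing radiograph taken at the appointment before randomisation". It says that the DMEC will look at these values for the NTB whenever it meets and may pass advice on training to the Trial Management Group.
- **Section 6.3 (Both braces)** provides for replacement: "Braces will be renewed when required due to growth of the child". It adds: "When a brace is renewed, the same protocol described above will be followed". An in-brace film, and hence a new correction value, therefore follows each renewal.

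Under Phase 1 of Section 9, an out-of-brace film is taken at each 6-monthly visit. The Trial Summary gives a mean time to skeletal maturity of 28 months (+/- 9) from a previous study with the same inclusion criteria.

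**The concern.** Section 9.4 states one fixed reference film, while 8.2 extends the measure to all new braces. For the first brace the two agree. For a later brace, the film named in 9.4 shows the curve as it was before randomisation, not the curve that the new brace has to correct. Any change since then enters the result.

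The error has a direction. If the curve has progressed, the value is too low; if it has improved, the value is too high. Progression is also what the primary outcome records, so replacement braces would score worst in the children whose curves are worsening, however well those braces fit. A DMEC looking for poorly made NTBs could then read progression as a fault in measurement or manufacture. The secondary outcome itself would also take different values depending on which section the analyst follows.

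**Working it through.** The protocol gives no numerical value for this measure, so there is no figure of its own to reproduce. The check compares the two reference films.

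**Inputs**

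- *B*, standing Cobb angle on the pre-randomisation film (the 9.4 reference). Eligibility allows 20 to 40 degrees (Section 5.1); 30 is assumed here.
- *C*, current standing out-of-brace angle when the brace is renewed. Assumed: 30, 35, 40 or 45 degrees.
- *c*, the share of the current curve that the new brace truly corrects. Assumed: 30%, 50% or 70%.
- *I*, the in-brace angle, equal to C × (1 − c).

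**Formulas**

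- Against the current film: (C − I) / C = c.
- Against the 9.4 film: (B − I) / B = 1 − (C / B) × (1 − c).
- Difference: (1 − c) × (C / B − 1). This is zero when C = B, grows with progression, and is larger for a brace that corrects less.

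**Worked case.** B = 30, C = 40, c = 50%, so I = 40 × 0.5 = 20.

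- Current film: (40 − 20) / 40 = 50.0%.
- 9.4 film: (30 − 20) / 30 = 33.3%.

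**Values read under 9.4, with B = 30**

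| True correction of current curve | C = 30 | C = 35 | C = 40 | C = 45 |
|---|---|---|---|---|
| 30% | 30.0% | 18.3% | 6.7% | −5.0% |
| 50% | 50.0% | 41.7% | 33.3% | 25.0% |
| 70% | 70.0% | 65.0% | 60.0% | 55.0% |

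The order of two braces can reverse. One that halves a curve now at 45 degrees reads 25.0%, below one that corrects only 30% of a curve still at 30 degrees (30.0%).

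The opposite case: B = 30, C = 25, c = 50%, so I = 12.5 and the 9.4 value is (30 − 12.5) / 30 = 58.3% instead of 50%.

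**First brace.** Section 9.2 places the screening film at day 0, fitting at weeks 4 to 8, and the in-brace film within 6 weeks of fitting, so no later than week 8 + 6 = 14 on the nominal timeline. The pre-randomisation film is then normally also the latest standing film before fitting, and both definitions use the same image.

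**The case against.** The best defence is that 9.4 was written with the first brace in mind. It comes soon after the timeline to the first 6-month appointment, does not mention renewals, and names a film that suits a first fitting. Section 8.2 names no film date, so the protocol does not set out two explicitly opposed references. The protocol also gives no renewal interval, so the age of the 9.4 film at renewal is unknown, and the curves used above are assumptions.

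Much of this is fair. The conflict is between one fixed film and a measure whose scope is every new brace. But 9.4 nowhere limits itself to the first brace. It gives one rule for the figure that the DMEC receives throughout the trial, and that rule, followed as written, gives a misleading value for a renewed brace.

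A reader might infer something stronger from film position: "The in-brace x-ray will be performed standing for FTB and supine for NTB". The background section states that "curves are 10 degrees smaller lying down compared to standing", so lying down alone would show 10/20 = 50%, 10/30 = 33.3% or 10/40 = 25.0% apparent correction for standing curves of 20, 30 and 40 degrees. It is tempting to conclude that the measure reflects posture rather than the brace, that it cannot reveal a poor NTB, or that it would flatter the NTB against the full-time brace. The documents do not support these conclusions:

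- The supine film is deliberate, since the NTB is worn lying down, and 9.4 says openly that NTB values will be higher for this reason.
- The protocol claims only that the measure reflects brace quality together with flexibility, and the in-brace angle still responds to the brace.
- The DMEC review is within the NTB arm, where every in-brace film is supine, and no pass mark is set that posture alone could meet.
- Section 11.2 plans no between-arm comparison of this measure.

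Nor would subtracting a flat 10 degrees help. A standing curve of 20 held at 8 is 60% raw and (10 − 8)/10 = 20% adjusted; a curve of 40 held at 20 is 50% raw and (30 − 20)/30 = 33.3% adjusted. The order reverses, and the adjustment adds a curve-size artefact of its own.

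**Conclusion.** The point holds for renewed braces. Used as written, the 9.4 reference makes their correction value fall as the curve progresses from baseline. For a true 50% correction and a 30-degree baseline, the shortfall is 8.3, 16.7 and 25.0 percentage points at current curves of 35, 40 and 45 degrees. For a true 30% correction it is 11.7, 23.3 and 35.0 points. These sizes rest on assumed curves; the direction follows from the formula alone. How many values are affected depends on how often braces are renewed and how far curves have moved by then, neither of which the protocol states.

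First-brace values are little affected. The primary outcome, the non-inferiority test and the sample size do not use this measure and are unaffected. It is a secondary outcome and a monitoring tool, so the fault is worth correcting but does not threaten the trial's main conclusion.

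**What to change.** In Section 9.4, define the reference separately for each brace: the latest out-of-brace standing film taken before that brace was fitted. For the first brace only, this is the pre-randomisation film. Add the same definition to the in-brace correction item in 8.2, so that the two sections agree, and use it in the DMEC reports. Recording the date of the reference film beside each value would let the DMEC see how old it is.

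The cost is a change of wording and of one derivation rule. The 6-monthly out-of-brace films are already planned, so no child needs an extra radiograph. Any renewed-brace values already calculated against the pre-randomisation film would need recalculating from stored images. One limitation remains: visits are nominally 6 months apart, with a window of 2 months either side, so the latest film may still miss some recent change. That gap is normally shorter than the time back to randomisation. No posture adjustment is needed.

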9.5 Procedure for assessing safety

Adverse events and serious adverse events are discussed in Section 10. If the site research team have any concerns about a participant's wellbeing or safety during the course of the trial, this will be flagged to the patient's usual clinical team.

9.6 Participant withdrawals

Excessive participant withdrawal from follow-up is likely to have a negative impact on the study. Centres will explain the importance of remaining on study follow-up to participants, and that changes to planned treatment need not imply withdrawal from the study. Nevertheless, if participants do not wish to remain in the study their decision must be respected and usual clinical care will continue.

Efforts will be made to keep participants engaged in study follow-up. Regular updates will be provided through newsletters, and prize draws will take place to include participants who complete follow up questionnaires. The follow-up visits have been aligned to the timescales of usual clinical follow-up to minimize the additional burden on participants. Most follow ups involve routine measures, with the addition of some patient completed questionnaires.

Participants may wish to withdraw from study treatment, or there may be a clinical need to withdraw the participant, such as development of a medical comorbidity which prevents further brace treatment.

Participants may withdraw their consent for the study at any time, without providing a reason for this. If this occurs, this will be documented on a study completion/discontinuation form and the patient notes, and no further data will be collected for this participant for the study. Although the participant is not required to give a reason for discontinuing their study treatment, a reasonable effort will be made to establish this reason while fully respecting the participants' rights. Any data collected up to the point of the participant's withdrawal will be retained, and used in the final analysis, and this is made clear to the patient at the time of consent. If a patient chooses to withdraw from the study, they will be asked if they are happy for the study team to use their routinely collected data in order to inform the primary outcome. This will be optional, but if the patient agrees, it will help to maintain the statistical power when assessing trial outcomes.

Guidance on cross-over can be found in section 6.4.

9.7 Loss to follow-up

Participants may be considered lost to follow up if they fail both to attend for a study visit and complete the corresponding visit questionnaires, and all reasonable efforts to contact the participant by different methods, including contact on different days/at different times, have been unsuccessful. If this occurs, the study team may liaise with the participant's clinical team to see whether they have also stopped attending clinical appointments. If a patient is still attending clinical appointments, this study visit will be marked as missing, and attempts will be made to contact the participant for the next study visit. If a participant fails to attend 2 study visits in a row, including non-completion of the corresponding questionnaires, they will be considered lost to follow up and this will be recorded on the study discontinuation form.

10. Safety Reporting

ICH-GCP requires that both investigators and sponsors follow specific procedures when reporting adverse events in clinical studies. These procedures are described in this section.

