11.2 Statistical Analysis

The trial will be analysed and reported according to CONSORT guidelines for noninferiority designs (54).

The ITT population (and safety) populations will consist of all participants who consent and are randomised to receive FTB or NTB.

The per protocol (PP) will be defined for participants in the FTB group, as

receiving the FTB treatment as documented in the study protocol (see Section 6)
 Complying and adhering to the treatment they were assigned to. Compliance with FTB would mean wearing the brace for average of >12.9hrs/day (= >65% of the minimum prescribed time) over the post-randomisation follow-up period.

For the NTB group, the PP population will be defined as

1) receiving the NTB treatment as documented in the study protocol

2) Complying and adhering to the treatment they were assigned to. Compliance with NTB would mean wearing the brace for average of >5.2hrs/day (= >65% of the minimum prescribed time) over the post-randomisation follow-up period.

Patients who cross-over from NTB to FTB will be removed from the PP population for the analysis of the primary outcome.

The binary primary outcome is curve progression to 50 degrees or more (treatment failure) before skeletal maturity and skeletal maturity without this degree of curve progression (treatment success). Non-inferiority for the primary outcome will be declared if the two-sided 95% confidence interval (equivalent to a one-sided 97.5%) for the risk difference in the event rate of progression to 50 degrees between the NTB group and the FTB group does not exceed 11%. The analysis will be completed using a Generalized Linear Model (GLM) with binomially distributed response and identity link (55) adjusted for baseline covariates (site, skeletal maturity Risser score 0, 1 or 2, and Cobb angle). This will be conducted on both an intention-to-treat (ITT) population and per protocol (PP) basis. The adjusted differences in failure rates, along with 95% con-fidence intervals will be calculated and presented.

Missing data

For the primary outcome, curve progression to 50 degrees or more (treatment failure) and skeletal maturity without this degree of curve progression (treatment success) any missing outcome data will be imputed through a default "worst" case scenario (i.e. assume treatment failure) and "best" case scenario (i.e. assume treatment success) and the results compared with the available data analysis.

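### Section 9.7 gives participants classed as lost after two missed visits no route to a later routine radiograph, so the primary outcome may be avoidably missing

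*Protocol*

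**What the plan says.** Section 9.7 works in two steps. After one missed visit the study team may ask the clinical team whether the child still comes to clinic: "If a patient is still attending clinical appointments, this study visit will be marked as missing", and contact is tried again for the next visit. The second step begins "If a participant fails to attend 2 study visits in a row, including non-completion of the corresponding questionnaires" and ends "they will be considered lost to follow up and this will be recorded on the study discontinuation form". It carries no exception for a child who still attends clinic, and it does not say what happens to radiographs taken later.

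Two neighbouring situations are handled differently:

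- **Withdrawal of consent (section 9.6).** The general consequence is that "no further data will be collected for this participant for the study". Participants are nevertheless asked whether they are "happy for the study team to use their routinely collected data in order to inform the primary outcome", and the stated reason is to protect statistical power.
- **Stopping the brace (section 9, Phase 1).** "If the patient stops bracing altogether, follow-up will be continued".

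Under section 8.1 the primary outcome is whether the curve reaches 50 degrees before skeletal maturity. Section 9 says it is measured on routinely collected out-of-brace radiographs. For participants without an outcome, section 11.2 says that "any missing outcome data will be imputed through a default" worst case (failure) and best case (success), with the results compared with the available-data analysis.

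**The concern.** The rule suits questionnaires, where a missed assessment cannot be recovered. It suits this primary outcome less well. The outcome is a status that may be settled well after two missed visits, and it is read from films that usual care produces anyway. A participant who has refused nothing, and who is X-rayed again in routine care, could be left without an outcome because a form has been completed and no one is told to look for the film.

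The protocol already accepts the principle in section 9.6, for people who have chosen to leave. It leaves the principle out for people who have not. At stake is the number of primary outcomes that have to be imputed in a non-inferiority comparison.

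**Working it through.** **Inputs.** Section 11.1: 28% failure on full-time bracing, 11-point margin, one-sided 2.5%, 90% power, 10% attrition, 780 participants (390 per arm). Section 9: visits every 6 months. Trial Summary: mean time to maturity 28 +/- 9 months. Equal failure in the night-time arm is assumed. The documents do not say how much of the 10% attrition would come from the two-visit rule.

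**1. The plan's own figure.** n per arm = (z₀.₉₇₅ + z₀.₉₀)² × 2p(1−p) / δ² = 10.507 × 2 × 0.28 × 0.72 / 0.11² = 10.507 × 0.4032 / 0.0121 = 350.1, so 351. Allowing for attrition: 351 / 0.90 = 390 per arm, 780 in total. The stated sample size reproduces exactly and is not in question.

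**2. Timing.** Two consecutive visits at 6-month spacing put the second missed visit about 12 months after the last one attended. Measured against the mean time to maturity, the status would be assigned:

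- at month 12 (visits 6 and 12 missed), 28 − 12 = 16 months before mean maturity;
- at month 18 (visits 12 and 18 missed), 28 − 18 = 10 months before;
- at month 24 (visits 18 and 24 missed), 28 − 24 = 4 months before.

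In each case the outcome may still lie ahead.

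**3. What a later film can settle.** A film at or before maturity shows whether 50 degrees has been reached by then. A mature film below 50 degrees generally establishes success. A first later film at 50 degrees or more taken after maturity may not show whether progression came before maturity. Recovery is therefore partial.

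**4. The three situations side by side.**

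| Situation | Refused anything? | Routine films for the primary outcome |
|---|---|---|
| Stops bracing (section 9) | No | Follow-up continues |
| Withdraws consent (section 9.6) | Yes | Asked; used if the participant agrees |
| Two missed visits and questionnaires (section 9.7) | No | Not stated |

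**5. Gain in power.** SE = √(2 × 0.28 × 0.72 / n); power = Φ(0.11 / SE − 1.96).

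- 10% loss, n = 351: SE = 0.0339, power 90.1%.
- 5% loss, n = 370.5 (half recovered, assumed): SE = 0.0330, power 91.5%.

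With losses above plan, 780 randomised would give 88.4% at 15% and 86.4% at 20%.

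**6. Reliance on imputation.** Take 28% failure among those observed. With a missing proportion d, the worst case gives 0.28(1 − d) + d and the best case 0.28(1 − d).

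- 10% missing in both arms: both become 35.2% (worst) or 25.2% (best). The risk difference moves by 0.
- 10% against 20% missing (assumed for illustration): worst case 42.4 − 35.2 = 7.2 points.
- The same pattern with half recovered (5% against 10%): worst case 35.2 − 31.6 = 3.6 points.

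Imputation distorts the comparison only if loss differs between arms, and then roughly in proportion to the amount missing.

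**The case against.** The strongest reply is that section 9.7 closes nothing. It attaches a label and names a form. The sentence ending data collection belongs to withdrawal of consent in section 9.6. Someone lost to follow-up has not withdrawn, so no special permission for routine data is needed. Section 8.1 starts committee review whenever the spinal team measures over 45 degrees or suspects maturity, and section 6.5 ties an offer of surgery to the committee's reading. Neither excludes a returning participant. The trigger also requires the questionnaires to be missed, and these are chased by mail or telephone. Because study visits follow usual care, two missed visits will often mean that no film exists for that period.

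Most of this stands. It rules out reading section 9.7 as a bar on later films. It does not remove the gap. Section 9.7 itself recognises that a child can miss study visits and still attend clinic, yet it applies that only to the first miss. Section 8.1 depends on staff acting for someone already recorded on a discontinuation form.

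Two stronger readings are tempting and unsupported. First, a reader might set missing night-time participants to failure and full-time participants to success, moving the difference by 10 points at 10% loss. Section 11.2 describes one worst case and one best case for any missing outcome and assigns nothing by arm; with equal loss the shift is 0. Second, a reader might infer that children tired of a full-time brace stop attending. Section 2.1 reports poor wear time, not poor attendance, and section 9 continues follow-up when bracing stops. Loss related to arm is possible but not shown.

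**Conclusion.** The point holds as a gap in wording, and closing it is a cheap improvement. Followed as written, the two-visit rule can leave the primary outcome avoidably missing for consenting participants, because the clinic-attendance check is not repeated and no routine-data route is given.

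The benefit is fewer missing primary outcomes and less dependence on worst- and best-case imputation. If half of the planned 10% loss were recovered, evaluable numbers would go from 351 to about 370 per arm and power from 90.1% to about 91.5%. That recovery rate is an assumption, as are equal true failure rates and attributing recoverable loss to this rule. The sample size is correct and needs no change. The protocol does not prohibit later films, and no bias in the non-inferiority result has been demonstrated.

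**What to change.** Add to section 9.7:

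- The status ends chasing for study visits and questionnaires only.
- Unless the participant refuses use of routine data, sites check records and send any later routine out-of-brace spinal radiograph through the existing image transfer route for blinded reading by the Radiographic Adjudication Committee, until the end of the trial.
- The primary outcome is classed as missing only at database freeze.

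The wording should also say how this fits with re-consent at age 16 in section 5.4, since some of these participants will pass that age while out of contact.

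The cost is a short protocol amendment and occasional record checks by site staff. The change uses films taken in usual care and asks for no additional radiographs. The transfer route and the committee already exist.
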